4.6. Safety Parameters

4.6.1. Adverse Events

AEs will be coded using MedDRA version 25.0 by preferred term (PT) within each system organ class (SOC).

4.6.1.1. Treatment-Emergent Adverse Events

A TEAE is any condition that was not present prior to treatment with study intervention but appeared following treatment, was present at treatment initiation but worsened during treatment, or was present at treatment initiation but resolved and then reappeared while the individual was on treatment (regardless of the intensity of the AE when the treatment was initiated).

4.6.1.2. Intensity of Adverse Events

Intensity (or severity) of AEs will be graded as follows:

- Mild
- Moderate
- Severe

For AEs with missing severity, the most severe assessment will be imputed for analyses, following worst case principle. If the intensity of an AE changes, then the most severe intensity during the continuous episode will be recorded.

4.6.1.3. Relationship to Study Intervention

The causal relationship with study intervention will be classified by the investigator and will be reported as follows:

- Not related
- Unlikely related
- Possibly related
- Probably related

Consider "probably related" and "possibly related" causality assessments as positive causality. "Not related" and "unlikely related" causality assessments are considered as negative causality.

Any missing relationship of an AE to study intervention will be considered as related to study intervention for the analyses, following worst-case principle.

4.6.2. Vital Signs and Clinical Laboratories

4.6.2.1. Laboratory Values

Clinical laboratory data (hematology, biochemistry and urinalysis) will be analyzed for observed value and change from baseline to 180/EOS/ET. Refer to Table 17 for the definition of baseline and Last.

In addition, participants reporting any sponsor-defined potentially clinically important (PCI) laboratory values during the study will be summarized.

PCI laboratory values are presented in Table 14.

Table 14: Potentially Clinically Important Laboratory values

Parameter	PCI Low ≤	PCI High ≥
Hemoglobin (g/L)	≤100	≥ 190
Hematocrit (%)	≤ 30	≥ 60
Platelets (10 ⁹ /L)	≤ 100	≥ 650
ALT (U/L)		\geq 3 × ULN
AST (U/L)		\geq 3 × ULN
Creatinine (µmol/L)		≥ 300
BUN (mmol/L)		≥ 12

ALT=Alanine transaminase; AST=Aspartate transaminase; BUN=Blood urea nitrogen; ULN=Upper limit of normal.

4.6.2.2. Vital Signs

Vital signs will be analyzed for observed value and change from baseline separately for vital signs on injection days and vital signs at each visit (excluding post injection time points on injection days). Refer to Table 17 for the definition of baseline.

In addition, participants reporting any sponsor-defined PCI vital sign values during the study will be summarized.

Vital sign values are PCI if they meet both the observed value criteria and the change from baseline criteria. The PCI vital sign values are presented in Table 15 below.

Table 15: Potentially Clinically Important Vital Sign Criteria

Parameter	PCI Low	PCI High	
Systolic blood pressure	≤90 mmHg and decrease ≥20 mmHg from baseline	≥180 mmHg and increase ≥20 mmHg from baseline	
Diastolic blood pressure	≤50 mmHg and decrease ≥15 mmHg from baseline	≥105 mmHg and increase ≥15 mmHg from baseline	
Pulse rate	≤50 bpm and decrease ≥15 bpm from baseline	≥120 bpm and increase ≥15 bpm from baseline	
Temperature		≥38.3°C and increase ≥1.1°C from baseline	

bpm=Beats per minute

5. ANALYSIS POPULATIONS

The study will use the following analysis populations for data summaries.

Table 16: Analysis Populations

Population Definition		Analysis	
Safety Population	The Safety Population is defined as all participants who received at least 1 injection of QWO (CCH-aaes).	All safety analyses will be based on this population	
Full Analysis Set (FAS)	The Full Analysis Set is defined as all participants in the Safety Population who have at least 1 valid IABSS assessment at a treatment area after an injection of QWO (CCH-aaes).	All efficacy analyses will be based on this population.	

6. STATISTICAL METHODS

6.1. General Methodology

All statistical tests, summary tables and data listings will be prepared using SAS version 9.4 or higher.

All statistical tests will be performed with a significance level of α =0.05, unless specified otherwise and will be supported by presenting estimates and 95% confidence intervals (CI).

Continuous data will be summarized using descriptive statistics. Discrete data will be summarized using frequency and percentages. The denominator will be based on the number of evaluable participants in the appropriate population.

For the purpose of display, the summary results will be rounded as follows:

- Minimum and maximum: same number of decimal places as the raw data
- Mean and Median: one decimal place more than the raw data
- Standard deviation (SD): Two decimal places more than the raw data
- Percentages will be displayed with one decimal place precision

For categorical variables with missing values, a category documenting the frequency of missing values will be displayed in the summary tables.

Summary tables, participant listings and any supportive SAS output will include footnotes that will indicate:

- Date of data extraction
- Date and time of output generation
- SAS program name, including the path, which generated the output

When calculating percentages, the denominator will be based on the number of participants with non-missing values. If the denominator is expected to change over time, then the denominator used to calculate the percentage will be based on the number of participants with non-missing

values at each visit. Any participant removed from an analysis will be noted at the bottom of the table along with the reason the participant was removed.

Empty summary tables will be presented with a note stating that "No Participants Met Criteria".

Participant listings of all data from the eCRFs as well as any derived variables will be presented.

6.2. Derived Variables

Table 17 defines the derived variables for study parameters.

Table 17: Derived Variables and Definition

Variable	Definition			
Age Group (years)	18 - <30 30 - <45 45 - 60			
Height (cm)	If height is recorded in inches, then height is equal to the recorded value multiplied by 2.54 and then rounded to 1 decimal place.			
Weight (kg)	If weight is recorded in pounds, then weight is equal to the recorded value multiplied by 0.454 and then rounded to 1 decimal place.			
Body Mass Index (BMI)	BMI will be computed using height measured at screening and body weight measured at respective visits as, BMI (kg/m^2) = Weight (kg) / Height $(m)^2$			
Relative Day	The day of first injection of study intervention will be considered as relative Day 1.			
Study Day (for assessment on or after Day 1)	Study Day will be computed as: Date of Assessment – Date of Day 1 + 1			
Study Day (for assessment before Day 1)	Study Day will be computed as: Date of Assessment – Date of Day 1			
Baseline	Baseline is defined as the last non-missing measurement/assessment prior to the first dose of study intervention. The assessments made in unscheduled visits will be considered in calculation of the baseline.			
Baseline for Vital Signs on Injection Days	For vital signs on injection days, the baseline value will be the vital sign measure immediately prior to the first dose of study intervention.			
Change from baseline	Change from baseline will be derived as: post baseline visit/time point value – the baseline value.			
Last (analysis)	Last is defined as the last non-missing measurement/assessment post the first dose of study drug intervention			
Duration (Minutes) of Exposure at each visit	Date/Time of Last Injection – Date/Time of First Injection			
Duration (Days) of AE	AE end date – AE start date + 1			
AE Start Day	AE start date – Date of Day 1 + 1			
AE Stop Day	AE end date – Date of Day 1 + 1			
Cellulite History (years) (≥ 5 or ≤ 5)	Day of Screening – Start Date of Cellulite History			

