4.4. Prior/Concomitant Medications and Procedures

All medications will be coded using World Health Organization (WHO) Drug Dictionary Version Global B3 March, 2022, by active ingredient and WHO anatomical therapeutic chemical (ATC) classification of ingredients.

• A prior medication/procedure is defined as any medication/procedure taken/done prior to first injection (Day 1).

• A concomitant medication (or non-drug therapy) is any medication (or therapy) taken on or after the Baseline Visit through the Day 180/EOS/ET Visit or the medication is reported as ongoing.

[figure not shown]
Please note that if a medication star.ted prior to Screening and end date is after screening/ongoing, it will be counted as both prior and concomitant medication.

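### AE days before Day 1 are numbered one day later than the SAP's own Study Day scale, and the concomitant-medication rules use conflicting cut dates

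*SAP*

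**What the plan says.** **AE days.** SAP 6.2, Table 17, fixes the origin of the scale: "The day of first injection of study intervention will be considered as relative Day 1". Study Day then has two formulas. From Day 1 onward 1 is added to the date difference. The second, headed "Study Day (for assessment before Day 1"), reads "Study Day will be computed as: Date of Assessment – Date of Day 1", so there is no Day 0. AE Start Day has one formula, "AE start date – Date of Day 1 + 1", and so has AE Stop Day, "AE end date – Date of Day 1 + 1". Neither has a form for dates before Day 1.

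**Concomitant medications.** SAP 4.4 defines a concomitant medication as "any medication (or therapy) taken on or after the Baseline Visit through the Day 180/EOS/ET Visit", or one reported as ongoing. A prior medication is one taken before the first injection on Day 1. A note in the same section then says that a drug started "prior to Screening and end date is after screening/ongoing, it will be counted as both prior and concomitant medication". SAP 6.3.1.2 adds rules for uncertain start dates:

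- First rule: start unknown, end after screening and before the Day 180/EOS/ET visit, or ongoing: concomitant.
- Second rule: start unknown, end before screening: not concomitant.
- Fourth rule: partial start date whose month and year precede the first injection: not concomitant. The end date is not consulted.

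**Cellulite history.** Table 17 labels this variable in years, with a split at 5, and defines it as "Day of Screening – Start Date of Cellulite History". It states no unit conversion.

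**The concern.** AEs are collected from consent (SAP 3.15), all AEs are listed (SAP 7.7.2), and listings carry derived variables (SAP 6.1). Events before Day 1 will therefore be printed with an AE day. In most cohorts a one-day shift there is cosmetic. In Cohort 7a it matters more, because tranexamic acid starts the day before the first injection. A reader using the listing to see whether an event came before or after the first tablet could be misled by the day number.

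For medications, Exclusion 4 lets a woman enter if she can stop antiplatelets, anticoagulants and similar drugs in time. Screening can be up to 28 days before Day 1, so a 14-day stop can fall wholly between the two. If a completed stop is tabulated as concomitant use, the table shows on-study exposure to a prohibited drug that bears on bruising, the outcome under study. The reverse error, an ongoing drug left out of the concomitant table, hides real on-study use.

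**Working it through.** **1. AE days**

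Inputs: the Study Day and AE Start/Stop Day formulas (SAP Table 17); Day 1 as the day of first injection (Table 17); tranexamic acid in Cohort 7a on Study Days -1, 1, 2, 3, 4 (Protocol 5.3, Figure 1), with Day -1 being the day before the first injection (SAP Table 2).

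Let k be the calendar date minus the date of Day 1.

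- Study Day = k + 1 if k ≥ 0, and k if k < 0.
- AE Start Day or AE Stop Day = k + 1 for every k.

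The plan's own figure first: the five consecutive dosing dates are k = -1, 0, 1, 2, 3. The Study Day rule gives -1, 1, 2, 3, 4, which matches Figure 1. The AE formula gives 0, 1, 2, 3, 4 for the same dates.

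| k | Study Day | AE day | Difference |
|---|---|---|---|
| -28 | -28 | -27 | +1 |
| -3 | -3 | -2 | +1 |
| -2 | -2 | -1 | +1 |
| -1 | -1 | 0 | +1 |
| 0 | 1 | 1 | 0 |
| 3 | 4 | 4 | 0 |

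The difference is (k + 1) - k = 1 for every date before Day 1, and zero from Day 1 onward. In Cohort 7a an event the day before the first tranexamic acid dose (k = -2) takes the label of the first dosing day, and an event on that dosing day (k = -1) takes a label that the study scale does not have.

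**2. Concomitant status**

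Assumption for illustration: Screening is 20 days before Day 1, and the Baseline Visit is Day 1. A drug stopped in screening is taken to end 8 days before Day 1. Any end date strictly between Screening and Day 1 gives the same result.

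| Drug | 4.4 definition | Other rule that applies |
|---|---|---|
| Started before Screening, stopped in screening | not concomitant | 4.4 note: concomitant |
| Start unknown, stopped in screening | not concomitant | 6.3.1.2 first rule: concomitant |
| Started and stopped before Screening | not concomitant | 4.4 note does not apply: agrees |
| Start unknown, stopped before Screening | not concomitant | 6.3.1.2 second rule: not concomitant |
| Known start and stop, both in screening | not concomitant | 4.4 note does not apply: agrees |
| Started before Screening, ongoing | concomitant | 4.4 note: concomitant |
| Partial start before first injection, ongoing | concomitant | 6.3.1.2 fourth rule: not concomitant |

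The rules conflict in the first, second and last rows: twice towards too much concomitant use, once towards too little.

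**3. Cellulite history**

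A difference of two dates is naturally a number of days, while the label says years. The class signs as printed (≥ 5 or ≤ 5) both include exactly 5.

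**The case against.** **Reach of the AE-day error.** TEAE status is decided from dates against the first injection (SAP 6.3.1.1), AE duration is computed from dates (Table 17), and AE summaries hold only TEAEs unless otherwise specified (SAP 7.7.2). The shift therefore reaches listings only. Listings also show all eCRF data, so the calendar dates stand beside the wrong day number. The tranexamic acid case concerns one sub-cohort of 15. All of this stands and keeps the point minor, but the printed day number is still wrong.

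**The formula's anchor.** A reader might infer that the AE formula counts from the wrong date. It does not: it uses the date of Day 1, as Study Day does. What is missing is the form for earlier dates.

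**Meaning of Baseline Visit.** Neither document defines the term. Protocol 11.1.3 places consent at Baseline, and Protocol 9.1.5 speaks of a baseline cellulite rating at Screening. If Baseline meant Screening, the 4.4 definition and note would agree. The other reading is better supported: Protocol 7.5 names the Screening and Baseline Visits separately, and the I-GAIS footnotes in the schedules equate Baseline with Day 1 before treatment. The note in 4.4 also follows a figure that cannot be read, so only the text is judged here.

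**Which drugs.** A reader might infer that any drug stopped before the first injection, or every 14-day washout, is misclassified. The rules do not support that. The 4.4 note reaches only drugs started before Screening, and the first rule of 6.3.1.2 only those with a wholly unknown start. Stop dates are recorded and a medication listing is planned, so a completed washout remains visible there.

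**Cellulite history.** A reader might infer that the variable will be analysed in days, too large by a factor of 365.25. The label says years, and a programmer would most likely convert. The code is in SAP Module 2, which is not among the documents. The overlapping class sign may be a text-conversion fault.

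**Conclusion.** The point holds within these limits.

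- **AE days:** every AE start or stop date before Day 1 is numbered exactly one day later than the SAP's Study Day scale. Later dates are correct. This follows from Table 17 without further assumption.
- **Medications:** a drug started before Screening, or with a wholly unknown start date, and stopped after Screening but before Day 1 counts as concomitant. This rests on reading the Baseline Visit as Day 1. The number of women affected cannot be derived from the documents. The fourth rule of 6.3.1.2 drops an ongoing drug with a partial start date before the first injection. That contradicts 4.4 on either reading of Baseline, because 4.4 counts ongoing drugs as concomitant.
- **Cellulite history:** a wording point only.

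SAP Table 18 does not list the AE-day formula or the Screening cut as an intended change. The consequences are confined to AE listings and the prior/concomitant medication tables. A reader might infer some effect on efficacy or on AE rates; the IABSS and I-GAIS analyses use none of these derivations, and AE counts do not depend on the AE day number. This is a minor correction.

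**What to change.** - **Table 17, AE Start Day and AE Stop Day:** use the two-part Study Day formula, with no +1 for dates before Day 1. An event two days before Day 1 then prints as -2, and one on the first tranexamic acid day in Cohort 7a as -1.
- **SAP 4.4 and 6.3.1.2:** define the Baseline Visit as Day 1 (first injection). Use that single cut, tested on the medication end date, in the 4.4 note and in the first, second and fourth rules of 6.3.1.2. A drug that ended before it is prior only; one that continues on or after it is concomitant.
- **Table 17, cellulite history:** state the conversion to years (days divided by 365.25) and use non-overlapping classes (<5 and ≥5 years).

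The cost is a few lines of SAP text and matching program changes. No data collection changes.

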6.3. Handling of Missing Data

Participants who withdraw from the study after the initiation of the study intervention will not be replaced and available data for these participants until the point of withdrawal will be summarized. However, the participants lost to follow-up at any time after the first dose of QWO (CCH-aaes) may be replaced.

Missing baseline assessments will not be imputed.

For categorical variables with missing values, a category documenting the frequency of missing values will be displayed in the summary tables.

There will be no imputation of missing values for safety data, however a missing relationship between AE and study intervention will be considered as related to study intervention following worst case principle. Missing severity of an AE will be summarized as a severe AE. Duration of the AE is classified in the '>21 Days" category if an AE is ongoing for more than 21 days by the last visit of the participant in the study.

6.3.1. Imputation of Partial Dates

6.3.1.1. TEAE Status for Completely Unknown Start Date

The following rules will apply in cases where start date of an AE is completely unknown:

- If the AE onset date is unknown and the end date is on or after first injection on Day 1 or ongoing, then the AE will be considered a TEAE.
- If the AE onset date is unknown and the end date is before first injection on Day 1, then the AE will not be considered a TEAE
- If both the start and end dates are unknown (or end date is ongoing), then the AE will be considered a TEAE, following the worst-case principle.
- If the AE onset date is partly present and month/year is prior to the first injection date, then the AE will not be considered a TEAE.

6.3.1.2. Concomitant Status of Medication for Completely Unknown Start Date

The following rules will apply in cases where start date of concomitant medication is completely unknown:

- If the medication onset date is unknown and the end date is after the screening date but before the Day 180/EOS/ET visit date or the medication is ongoing, then the medication will be considered as concomitant.
- If the medication onset date is unknown and the end date is before the screening date, then the medication will not be considered as concomitant.
- If both the start and end dates are unknown, then the medication will be considered as concomitant. This approach is considered to be the most conservative following the worst-case principle.
- If the medication onset date is partly present and month/year is prior to the first injection date, then the medication will not be considered as concomitant.

6.3.1.3. Missing Last Menstrual Date

Missing date of last menstrual period will be imputed with the last day of the month and missing onset month will be imputed with December.

6.4. Interim Analysis

No interim analysis is planned for this study.

6.5. Stopping Rules for Study

The sponsor has the right to suspend or terminate the study at any time. The study may be suspended or terminated for any reason.

7. STATISTICAL ANALYSES

7.1. Participant Disposition

The number of participants included in each study population will be summarized by each cohort and overall. Participants excluded from the Safety Population and FAS will be listed.

The frequency and percentages of participants screened, enrolled, completed, and/or withdrawn from the study, as well as the reason for withdrawal from study will be summarized by each cohort and overall.

A listing of disposition data will be provided. Screen failure reasons will also be listed. In addition, listing for inclusion/exclusion criteria will also be presented.

7.2. Protocol Deviations

Protocol deviations will be summarized by deviation classification (important/not important), for each of the 7 cohorts and overall. A listing of all protocol deviations will be presented.

7.3. Demographics and Baseline Characteristics

Demographic and baseline characteristics will be summarized by overall and each cohort for both the Safety Population and FAS. Refer to Table 14 for the list of parameters.

All the continuous variables will be summarized using descriptive statistics. Rest of the categorical variables will be summarized by frequency and percentages.

The following baseline characteristics will be summarized using frequency and percentages:

- CR-PCSS cellulite severity ratings for buttock by visit (mean and SD will also be provided).
- Hexsel CSS scores by visit (mean and SD will also be provided).
- IABSS by visit (mean and SD will also be provided).

All demographic and baseline characteristics will be presented in participant listings.

7.4. Medical and Surgical History

Medical history will be coded using MedDRA version 25.0. Medical and surgical history data will not be summarized; however, a participant listing will be provided.

7.5. Prior/Concomitant Medications and Procedures

Prior and concomitant medications will be summarized by each cohort and overall using frequency and percentages by active ingredient within each ATC, with ATC and active ingredients ordered alphabetically. Prior and concomitant procedures (nondrug therapies) will be summarized by each cohort and overall using frequency and percentages with name of the procedures ordered alphabetically. Multiple uses of the same medication/procedure by a participant will be counted only once.

A participant listing of medications indicating prior and concomitant medications and procedures will be provided. Similarly, only listing for cellulite history will also be presented.

7.6. Efficacy Analyses

Efficacy parameters will be summarized for each treatment areas for each cohort using the FAS.

7.6.1. Primary Analysis

7.6.1.1. Cohort 1-6: The proportion of one-level IABSS responders, at Visit 3, three to five days after initial QWO (CCH-aaes) injection.

The primary estimand for cohort 1 to 6 is defined by the following:

- The *primary* clinical question of interest is: In adult female participants with moderate to severe cellulite, what is the proportion of participants in Cohort 1-6, whose left buttock (investigational side) demonstrates at least 1-level lower IABSS score versus the right buttock (control side) on the IABSS, at Visit 3, 3 to 5 days after initial QWO (CCH-aaes) injection?
- **Treatment condition:** Participants will be assigned to 1 of 6 cohorts.
- Target Population: Adult females with a CR-PCSS score of 3 or 4 on both buttocks, Hexsel CSS \leq 12, with a BMI of 18 to < 32 kg/m² (normal or overweight) and Fitzpatrick skin type of I-IV who are included in the FAS.
- Variable (Endpoint) of interest: Proportion of one-level IABSS responders at Visit 3, 3 to 5 days after initial QWO (CCH-aaes) injection for Cohort 1-6. Refer to Section 4.5.1 for one-level IABSS responder definition.
- Treatments being compared: The labelled dose and concentration will be compared to administering the labelled dose or lower doses in different diluent additives, concentrations, depths of injection, and methods of injection (refer to Table 2).
- Intercurrent Event: Not applicable.
- **Population Level-Summary measure:** Not applicable.

- **Method of Analyses:** The one-level IABSS responders will be summarized for each cohort using frequency, proportion and corresponding 95% CI based on the Clopper-Pearson method for one-level IABSS responders at Visit 3, 3 to 5 days after the initial QWO (CCH-aaes) injection for Cohort 1-6.
- Supportive analysis to primary endpoint: Not applicable.

IABSS ratings will be summarized by treatment area at each visit for all 7 cohorts and overall. A listing of IABSS ratings by participant will be provided.

7.6.1.2. Cohort 7a: The proportion of one-level IABSS responders, at Visit 3 versus Visit 8, three to five days after initial QWO (CCH-aaes) injection at respective visit.

The primary estimand for cohort 7a is defined by the following:

- The *primary* clinical question of interest is: In adult female participants with moderate to severe cellulite, what is the proportion of participants in Cohort 7a whose left buttock (investigational side), at Visit 3, demonstrates at least 1-level lower IABSS score versus the right buttock (control side), at Visit 8?
- **Treatment condition:** Participants will be assigned to Cohort 7a.
- Target Population: Adult females with a CR-PCSS score of 3 or 4 on both buttocks, Hexsel CSS ≤ 12, with a BMI of 18 to < 32 kg/m² (normal or overweight) and Fitzpatrick skin type of I-IV who are included in the FAS.
- Variable (Endpoint) of interest: Proportion of one-level IABSS responders at Visit 3 versus Visit 8, 3 to 5 days after initial QWO (CCH-aaes) injection for each respective visit for Cohort 7a. Refer to Section 4.5.1 for one-Level IABSS responder definition.
- Treatments being compared: The labelled dose and concentration will be compared to administering the labelled dose or lower doses in different diluent additives, concentrations, depths of injection, and methods of injection (refer to Table 2).
- Intercurrent Event: Not applicable.
- **Population Level-Summary measure:** Not applicable.
- **Method of Analyses:** The one-level IABSS responders will be summarized for each cohort using frequency, proportion and corresponding 95% CI based on the Clopper-Pearson method for one-level IABSS responders at Visit 3 versus Visit 8, 3 to 5 days after initial QWO (CCH-aaes) injection for each respective visit for Cohort 7a.
- Supportive analysis to primary endpoint: Not applicable.

7.6.1.3. Cohort 7b: The proportion of one-level IABSS responders, at Visit 8 versus Visit 3, three to five days after initial QWO (CCH-aaes) injection at respective visit.

The primary estimand for Cohort 7b is defined by the following:

- The *primary* clinical question of interest is: In adult female participants with moderate to severe cellulite, what is the proportion of participants in Cohort 7b whose left buttock (investigational side), at Visit 8, demonstrates at least 1-level lower IABSS score versus the right buttock (control side), at Visit 3?
- **Treatment condition:** Participants will be assigned to Cohort 7b.
- **Target Population:** Adult females with a CR-PCSS score of 3 or 4 on both buttocks, Hexsel CSS ≤ 12, with a BMI of 18 to < 32 kg/m² (normal or overweight) and Fitzpatrick skin type of I-IV who are included in the FAS.
- Variable (Endpoint) of interest: Proportion of one-level IABSS responders at Visit 8 versus Visit 3, 3 to 5 days after initial QWO (CCH-aaes) injection for each respective visit for Cohort 7b. Refer to Section 4.5.1 for one-Level IABSS responder definition.
- **Treatments being compared:** The labelled dose and concentration will be compared to administering the labelled dose or lower doses in different diluent additives, concentrations, depths of injection, and methods of injection (refer to Table 2).
- Intercurrent Event: Not applicable.
- Population Level-Summary measure: Not applicable.
- **Method of Analyses:** The one-level IABSS responders will be summarized for each cohort using frequency, proportion and corresponding 95% CI based on the Clopper-Pearson method for one-level IABSS responders at Visit 8 versus Visit 3, 3 to 5 days after initial QWO (CCH-aaes) injection for each respective visit for Cohort 7b.
- Supportive analysis to primary endpoint: Not applicable.

